#### **Response Measures:**

##### *Safety assessments:*

- Adverse Events (AEs)
- ETDRS BCVA
- Intraocular pressure (IOP)
- Slit lamp biomicroscopy
- Dilated fundus exam (DFE)
- Crystalline lens assessment using AREDS scale
- Post-injection assessment
- Laboratory evaluation (hematology, serum chemistry and urinalysis)
- Electrocardiogram (ECG)
- Vital signs
- Physical examination
- Pregnancy test

*Efficacy assessments:*

- Improvements in ETDRS BCVA
- SD-OCT (Heidelberg Spectralis, dense scan) as measured by Central Reading Center (CRC)
  - Central subfield thickness (CST)
  - Ellipsoid zone (EZ)
  - External limiting membrane (ELM)
  - Intraretinal and subretinal fluid
  - Posterior vitreous detachment
- OCT-A as measured by CRC
  - Foveal avascular zone (FAZ)
  - Foveal capillary density (CD) (superficial and deep capillary plexuses)
- Diabetic retinopathy severity score (DRSS) assessed via color fundus photography
- Time to rescue medication

*Pharmacokinetics:* Plasma concentrations of AG-73305.

*Immunogenicity:* Serum levels of anti-AG-73305 antibodies (using binding and neutralizing antibody assays, if available).

**Study Population:** Approximately 25, adult male or female patients with center involving DME in the study eye will participate in the study, including a sentinel patient in each of 4 dose cohorts (see [Figure 1](#)).

**Phase:** 2a

**Description of Sites:** Approximately 8 sites in the United States will enroll patients.

**Description of Study Treatment:** AG-73305 is a humanized IgG1 Fc-fusion protein that targets vascular endothelial growth factors, placental growth factors and integrins. AG-73305 is a clear solution formulated in a 40 mg/mL concentration for intravitreal injection. Ascending doses of a single injection of AG-73305 will be assigned by cohort to 0.5, 1, 2, and 4 mg or until the maximally tolerated (or maximum administered) dose has been reached (see [Table 1](#)).

**Rescue Medication** will be standard-of-care anti-vascular endothelial growth factor (VEGF) administered by IVT in the study eye. Rescue medication is allowed at the Week 4 visit or later in patients meeting any of the following criteria:

- Loss of > 10 ETDRS letters from a previous best study visit with worsening of intraretinal or subretinal fluid observed by SD-OCT and judged by the Investigator to be the cause of the BCVA loss.

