Immunogenicity: Serum levels of anti-AG-73305 antibodies (using binding and neutralizing antibody assays, if available).

Study Population: Approximately 25, adult male or female patients with center involving DME in the study eye will participate in the study, including a sentinel patient in each of 4 dose cohorts.

Phase: 2a

Description of Sites: Approximately 8 sites in the United States will enroll patients.

Description of Study Treatment: AG-73305 is a humanized IgG1 Fc-fusion protein that targets vascular endothelial growth factors, placental growth factors and integrins. AG-73305 is a clear solution formulated in a 40 mg/mL concentration for intravitreal injection. Ascending doses of a single injection of AG-73305 will be assigned by cohort to 0.5, 1, 2, and 4 mg or until the maximally tolerated (or maximum administered) dose has been reached (see Table 1).

Rescue Medication will be standard-of-care anti-vascular endothelial growth factor (VEGF) administered by IVT in the study eye. Rescue medication is allowed at the Week 4 visit or later in patients meeting any of the following criteria:

- Loss of > 10 ETDRS letters from a previous best study visit with worsening of intraretinal or subretinal fluid observed by SD-OCT and judged by the Investigator to be the cause of the BCVA loss.
- Loss of > 5 ETDRS letters at 2 consecutive visits (one can be unscheduled) from a previous best study visit due to worsening of DME.
- An increase in CST > 75 μ m from a previous best study visit which remains consistently > 75 μ m from the previous best study in two consecutive visits, as assessed by SD-OCT.

The later visit can be an unscheduled visit if determined to be necessary by the Investigator.

- An increase in CST $> 50 \mu\text{m}$ from a previous best study visit, as assessed by SD-OCT and a loss of > 5 ETDRS letters, which remains consistently $> 50 \mu\text{m}$ and loss > 5 ETDRS letters from the previous best study in two consecutive visits. The later visit can be an unscheduled visit if determined to be necessary by the Investigator.
- Progression of or worsening of proliferative diabetic retinopathy.

Patients will be followed for at least 4 weeks after Rescue medication administration or through Week 12, whichever is greater.

Table 1: Summary of Open-label Cohorts and Dosing

Dose (mg)	Stock Vial Concentration (mg/mL)	Dilution Requirement	Volume to be Injected (mL)
0.5	40	1:1 with diluent	0.025
1	40	None	0.025
2	40	None	0.050
4	40	None	0.100

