Randomization: none

Study Duration: The anticipated study duration is approximately 52 weeks, including 24 weeks for recruitment, up to 4 weeks for screening and 24 weeks of follow-up after administration of a single intravitreal injection of AG-73305. In certain cases, screening may be increased to 6 weeks, for a total of 54 weeks for the study duration.

Patient Duration: 28 weeks participation for patients from Screening to Exit. For patients where screening is increased to 6 weeks, then a total of 30 weeks of participation is expected.

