9.5.1.3.2. Secondary Efficacy Assessments

Dilated color fundus photography will be performed OU at the Baseline Visit, in the SE at Week 4, and OU at Week 24 to assess diabetic retinopathy severity score (DRSS).

Spectral Domain Optical Coherence Tomography (SD-OCT) will be performed OU at each in-clinic visit (Heidelberg Spectralis, dense scan). SD-OCT will assess central subfield thickness (CST), ellipsoid zone (EZ), external limiting membrane (ELM), intraretinal and subretinal fluid volume, and posterior vitreous detachment.

OCT Angiography (OCT-A) will be performed OU at the Baseline Visit, in the SE at Weeks 4 and 24, and OU at the visit when Rescue treatment is given. OCT-A will assess foveal avascular zone (FAZ) and foveal capillary density (CD) (superficial and deep capillary plexuses).

Color fundus photos and SD-OCT and OCT-A images will be submitted to a central reading center for grading.

Time to rescue medication will be assessed. Rescue medication will be standard-of-care anti-vascular endothelial growth factor (VEGF) administered by intravitreal injection (IVT) in the

study eye. Rescue medication is allowed at the Week 4 visit or later in patients meeting any of the criteria outlined in the protocol Section 6.5.3.

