9.7.1.2. Analysis of Patient Disposition

The number of patients enrolled at each site will be summarized by treatment cohort and overall using the FAS.

Patients' enrollment and disposition during the study will be summarized by treatment cohort and overall using the FAS. The reasons for discontinuation will be displayed in the order as they appear on the eCRF, and percentages will be calculated based on the number of patients who discontinued the study.

Summary tables will include the following. The percentages will be calculated based on the number of patients in the FAS.

- Number of patients screened
- Number and percentage of patients treated
- Number and percentage of patients treated who completed the study
- Number and percentage of patients treated who discontinued from the study
- The reasons for study discontinuation
- Number and percentage of patients attending each scheduled study visit

A listing of patients who do not meet all inclusion criteria or meet exclusion criteria will be provided. A table of major protocol deviations will be presented using the FAS.

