9.7.1.5.2. Secondary Efficacy Analyses

Observed and change from baseline in CST as measured by SD-OCT at Week 1, 4, 8, 12, 16, 20 and 24 will be presented. A change from baseline in CST will indicate a positive response if the treatment difference is < 0 . Observed and change in intraretinal and subretinal fluid volumes, ELM and EZ by SD-OCT at each visit will also be presented. The presence of posterior vitreous detachment will be summarized by frequency and percentage.

Observed and change from baseline in FAZ and CD of the superficial and the deep capillary plexuses will be presented, as measured by OCT-A at the Baseline Visit, Week 4, and Week 24.

Observed and change from baseline in DRSS will be presented, assessed via color fundus photography at the Baseline Visit, Week 4, and Week 24.

Time from Day 1/Baseline to receipt of rescue medication in the study eye will be analyzed using Kaplan-Meier time-to-event analyses. Follow-up is measured to the earliest instance of receipt of rescue therapy in the study eye for patients receiving rescue therapy. Otherwise, patients are censored at the date they complete or discontinue the study. In addition, reasons for rescue and use of rescue medication by visit will be summarized by frequency and percentage. Rescue will be included at Visit X if the date rescue is provided is on or after Visit X and before Visit X + 1.

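### The time-to-rescue analysis censors every discontinuation whatever its reason, so if a patient leaves unrescued because the study eye worsened, the rescue-free curve will look too favourable as a measure of duration of effect

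*SAP*

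**What the plan says.** The analysis is defined in SAP 9.7.1.5.2: "Time from Day 1/Baseline to receipt of rescue medication in the study eye will be analyzed using Kaplan-Meier time-to-event analyses". The event is the first rescue: "Follow-up is measured to the earliest instance of receipt of rescue therapy in the study eye for patients receiving rescue therapy". For everyone else, "Otherwise, patients are censored at the date they complete or discontinue the study". Discontinuation is not split by reason.

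Rescue has an opening date. The protocol synopsis says "Rescue medication is allowed at the Week 4 visit or later in patients meeting any of the following criteria", and SAP 9.5.1.3.2 repeats the restriction by reference to protocol Section 6.5.3. In the protocol's Schedule of Activities (1.3) the Week 4 visit is Day 28 ± 5, so it can fall as early as Day 23. Patients who are not rescued are followed for 24 weeks.

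Reasons for leaving are collected. SAP 9.7.1.2 says "The reasons for discontinuation will be displayed in the order as they appear on the eCRF". They feed the disposition table only. SAP 9.7.1 limits analyses to observed data, 9.7.1.5.3 plans no exploratory efficacy analysis, and no sensitivity, composite or competing-event version of the time-to-rescue analysis appears.

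**The concern.** Kaplan-Meier treats a censored patient as having the same later rescue risk as those still under observation. That is reasonable for a patient who moves away. It is not reasonable for one who leaves because the treated eye is getting worse: that patient's effect has probably ended, yet the method gives them the average prospects of those who stayed.

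The Week 4 opening sharpens this. Before it, a worsening patient who stays cannot yet receive rescue under the plan, and one who leaves is censored before any permitted event can occur.

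The stake is the duration-of-effect objective (protocol synopsis; SAP 9.5.1). Time to rescue is the SAP's only time-to-event analysis, efficacy is presented by cohort (9.7.1.5), and cohorts hold 3 to 8 patients (9.7.2), so one patient can move the curve visibly.

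**Working it through.** **Inputs.** The event and censoring rules are from SAP 9.7.1.5.2, the Week 4 opening from the protocol synopsis and SAP 9.5.1.3.2, and cohort sizes 3, 6 and 8 from SAP 9.7.2. The documents give no dropout rate, rescue rate or projected time to rescue, so there is no plan figure to reproduce for this endpoint. The numbers of leavers and rescues below are assumptions.

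**Step 1: an early leaver drops out of the estimate.** Kaplan-Meier multiplies (1 − events / number at risk) over the event times. A patient censored before the cohort's first rescue is in no risk set at an event time, so the curve is the same as if that patient had never been enrolled.

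**Step 2: one early leaver, r later rescues, no other censoring up to the time of interest.**

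- As planned: (n − 1 − r) / (n − 1)
- Leaver counted as a failure: (n − 1 − r) / n
- Gap: (n − 1 − r) / [n(n − 1)], which is the planned estimate divided by n

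| n | r | As planned | Counted as failure | Gap (points) |
|---|---|---|---|---|
| 3 | 0 | 2/2 = 100% | 2/3 = 67% | 33 |
| 3 | 1 | 1/2 = 50% | 1/3 = 33% | 17 |
| 6 | 0 | 5/5 = 100% | 5/6 = 83% | 17 |
| 6 | 1 | 4/5 = 80% | 4/6 = 67% | 13 |
| 6 | 2 | 3/5 = 60% | 3/6 = 50% | 10 |
| 6 | 3 | 2/5 = 40% | 2/6 = 33% | 7 |
| 6 | 4 | 1/5 = 20% | 1/6 = 17% | 3 |
| 8 | 0 | 7/7 = 100% | 7/8 = 87.5% | 12.5 |
| 8 | 1 | 6/7 = 86% | 6/8 = 75% | 11 |
| 8 | 2 | 5/7 = 71% | 5/8 = 62.5% | 9 |
| 8 | 3 | 4/7 = 57% | 4/8 = 50% | 7 |
| 8 | 4 | 3/7 = 43% | 3/8 = 37.5% | 5 |

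The planned rule credits the leaver with the cohort's average rescue-free probability; the alternative credits zero. The gap therefore closes as rescues accumulate. With L early leavers the ratio of the two estimates is n / (n − L): for n = 6, 1.20 with one and 1.50 with two; with none it is 1.

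**Step 3: effect on a median.** Take n = 6, one leaver on Day 14, and rescues on Days 56, 84 and 112. At Day 84 the planned estimate is 4/5 × 3/4 = 60%; with the leaver as an event it is 5/6 × 4/5 × 3/4 = 50%. Taking the median as the first time the curve is at or below 50%, it is Day 112 as planned and Day 84 otherwise. Averaging across the flat stretch at exactly 50% would make the second figure (84 + 112) / 2 = Day 98.

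**Step 4: a later leaver.** This patient counts until exit and is treated as average afterwards. Take n = 6 with one rescue, then the leaver, then a second rescue. As planned: 5/6 × 3/4 = 62.5%. Leaver as an event: 5/6 × 4/5 × 3/4 = 50%.

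**Step 5: average size in a large sample.** Assume an exponential time to need for rescue with median 84 days, rescue given at the next four-weekly visit from Day 28, and that a share q of those who fail before Day 28 leave. The fraction failing before Day 28 is 1 − 2^(−28/84) = 0.206. The rescue-free probability at Day 84 is 0.50, and the planned analysis estimates 0.50 / (1 − 0.206q). For q = 10%, 25%, 50% and 100% this gives 0.51, 0.53, 0.56 and 0.63.

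**Not affected.** Rescued patients may have shorter follow-up ("Patients will be followed for at least 4 weeks after Rescue medication administration or through Week 12, whichever is greater"), but they are already events, so this does not touch the curve.

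**The case against.** The strongest reply is that nothing shows the problem will arise. No dropout rate is given, and nothing says that patients will leave for worsening. The exposed period before rescue opens is only about three to four weeks; after that, a worsening patient who stays and meets a rescue criterion can be treated and becomes an event. The endpoint is secondary and descriptive, in non-randomized cohorts with no power basis. Disposition reasons, listings and an early-termination visit with acuity and OCT would let a careful reader trace each leaver. Counting withdrawal as an event also changes what is measured, so part of each gap in the table is a difference of definition.

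Most of this limits the size and the remedy. It does not answer the point, because disposition tables and listings do not correct the curve and no planned analysis shows how far it depends on the censoring rule.

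Three stronger readings are tempting but unsupported:

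- **Early treatment is obtainable only by leaving.** This is an inference from the Week 4 rule. Protocol Section 6.5.3 and the withdrawal rules are not in the text available, and the event definition does not exclude rescue given early as a deviation to a patient who stays.
- **The ranking of doses will be distorted.** No ranking on this curve is planned. The dose objective concerns the highest dose tolerated or given.
- **Such leavers can be identified from the eCRF.** The SAP says that reasons are recorded but does not list them. A patient leaving for treatment elsewhere might appear only as a withdrawal of consent.

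**Conclusion.** The point holds in conditional form. If a patient leaves unrescued because the study eye worsened, the planned curve is too high as a measure of duration of effect. A reader might infer that time to rescue is already overstated. The documents do not support that, since without such a leaver there is no bias.

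With one early leaver the gap runs from 33 points (cohort of 3, no rescues) to 3 points (cohort of 6, four rescues). These figures assume no other censoring and treat the leaver as a certain failure. Under the large-sample assumptions above, the average effect is 1 to 6 points if up to half of the early failures leave, and 13 if all do.

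No error rate or sample size is affected. The case is for a cheap supplementary analysis and does not require replacing the endpoint.

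**What to change.** Keep the receipt-of-rescue curve as the main analysis. In SAP 9.7.1.5.2 add:

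1. A supplementary Kaplan-Meier curve by cohort, in which discontinuation without rescue for lack of efficacy or study-eye worsening is an event at the discontinuation date. Other discontinuations stay censored.
2. A mapping of those two reasons to the actual eCRF categories, fixed before the data are reviewed. The study is open-label with periodic data review, so the date of the mapping should be recorded.
3. A short table of censored patients by cohort, reason and time of censoring.

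The cost is a few sentences, one extra curve and one small table, with possibly less favourable rescue-free figures. If nobody leaves for worsening, the two curves coincide. The change concerns the analysis only; when rescue may be given is not in question.

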9.7.1.5.3. Exploratory Efficacy Analysis

Not applicable.

9.7.1.6. Analysis of Safety

Safety will be evaluated by:

1. Adverse event (AE) monitoring (study eye and fellow eye)
2. ETDRS BCVA
3. Intraocular pressure (IOP)
4. Slit lamp biomicroscopy, including crystalline lens assessment using AREDS scale
5. Dilated fundus exam (DFE)
6. Post-injection assessment
7. Laboratory evaluation (hematology, serum chemistry and urinalysis)
8. Electrocardiogram (ECG)
9. Vital signs
10. Pregnancy test

The FAS will be used for all safety analyses. All data will be summarized as observed and no data imputation will be performed. No statistical treatment group comparisons will be performed, unless otherwise specified. Analyses will be presented by cohort and by study eye and non-study eye, if applicable.

Results from the physical examination performed at Screening will be presented in a listing.

All safety data will be censored (set to missing) on or after the earliest instance of rescue therapy when summarized in tables. All data will be presented in listings. This will impact the definition of TEAE.

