9.7.1.6.1. Adverse Events

AEs are coded using MedDRA Version 25.0. Treatment-emergent adverse events (TEAE) are defined as events that start on or after the administration of study medication and up to the earliest instance of rescue therapy. Pretreatment adverse events are events that begin prior to administration of study medication. Ocular AEs are defined as those events for which an eye has been specified (OD, OS, or OU).

Ocular and non-ocular treatment-emergent AEs will be summarized separately. Ocular AEs will be presented by study eye and non-study eye and overall (OU) if an event occurs in either eye.

In all summaries of AEs, percentages are calculated based on the number of patients in each treatment group of the Safety Analysis Set.

Overall summaries of AEs by treatment will include:

- the number of AEs and SAEs reported;
- the number and percentage of patients who experienced any AE;

- the number and percentage of patients who experienced any serious adverse event (SAE) and the reason for seriousness;
- the number and percentage of patients with any AE by worst severity and worst relationship.

The overall summaries of TEAEs will also include the number and percentage of patients with any TEAEs leading to study termination.

Summaries of the frequency and percentage of patients with AEs by SOC and preferred term by treatment group will include:

- All AEs by SOC and preferred term;
- All AEs by SOC, preferred term, and maximum severity;
- All AEs by SOC, preferred term, and maximum relationship.

System organ class (SOC) will be sorted alphabetically, and preferred term (PT) within each SOC will be sorted by overall descending order of frequency according to the following rules in order:

1. Descending frequency within AG-73305, 0.5 mg;
2. Descending frequency within AG-73305, 1 mg;
3. Descending frequency within AG-73305, 2 mg;
4. Descending frequency within AG-73305, 4 mg;
5. PT in alphabetical order.

Patients are counted only once for each SOC and PT. In summaries of maximum severity and maximum relationship, patients with multiple occurrences of events will only be counted once at the maximum severity/relationship per SOC and PT.

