Any treatment-emergent AEs that have a missing severity will be presented as severe in the summary table but will be presented with a missing severity in the data listing. Any treatment-emergent AEs that have a missing relationship will be presented as “Related” in the summary table but will be presented with a missing relationship in the data listing.

All AEs are displayed in listings. In addition, separate listings will be provided for:

- Patients with any treatment-emergent adverse event leading to study termination;
- Patients with any serious adverse event (treatment-emergent or otherwise);
- Patient deaths.

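### Safety tables drop all data from the first rescue onward, and no table is stated to cover the follow-up the protocol requires after it

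*SAP*

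**What the plan says.** **SAP 9.7.1.6 (Analysis of Safety).** "The FAS will be used for all safety analyses". The closing paragraph then sets the rule: "All safety data will be censored (set to missing) on or after the earliest instance of rescue therapy when summarized in tables". It sends the complete data to listings and adds: "This will impact the definition of TEAE".

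**SAP 9.7.1.6.1 (Adverse Events).** TEAEs are "events that start on or after the administration of study medication and up to the earliest instance of rescue therapy"; pretreatment AEs are those that begin before study drug. The overall summaries include "the number and percentage of patients with any AE by worst severity and worst relationship", and the tables by body system begin with "All AEs by SOC and preferred term". The section does not say whether post-rescue events count in these. Percentages are based on a Safety Analysis Set, which section 9.7.1.1.1 does not define; the only set defined there is the FAS. Listings cover all AEs, all SAEs whether or not treatment-emergent, and deaths.

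**Protocol 1.1 (Synopsis, Rescue Medication).** Rescue is an anti-VEGF injection into the study eye, permitted from the Week 4 visit. Follow-up then continues for at least four weeks or to Week 12, whichever comes later.

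**SAP 9.7.1.5.2.** Rescue is counted at Visit X "if the date rescue is provided is on or after Visit X and before Visit X + 1", so rescue on the day of a visit is foreseen.

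**The concern.** Safety data after rescue are collected by design and then left out of every safety table as the rule is worded. The cut is not confined to the eye that received the other drug: fellow-eye findings, non-ocular AEs, laboratory values, ECGs, vital signs and SAEs all stop at the same moment.

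The protocol's safety hypothesis is framed in terms of AE incidence and severity. Removing events from the numerator while keeping the patient in the denominator moves both in one direction only. Because rescue follows worsening vision, retinal thickness or retinopathy, a cohort rescued earlier or more often has a shorter tabulated window. Cohort columns read side by side may then cover unequal periods.

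**Working it through.** **1. The plan's own figure.** SAP Table 2 (section 9.7.2) gives the chance of at least one patient with a DLT or SAE as 1 − (1 − p)^n. For p = 0.2 this is 1 − 0.8³ = 0.488, 1 − 0.8⁶ = 0.738 and 1 − 0.8⁸ = 0.832, as printed. All 24 cells agree to within 0.0005.

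**2. Which tables are cut.** Section 9.7.1.6 covers all safety data in tables. Section 9.7.1.6.1 speaks separately of AEs and TEAEs, so its AE tables could be read as uncut. The general sentence is taken to govern, because it makes no exception. An AE starting after rescue is then neither treatment-emergent nor pretreatment.

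**3. Collected time left untabulated.** For rescue at week r, minimum follow-up is f = max(r + 4, 12) and the untabulated share is (f − r)/f. If the patient stays to Week 24 it is (24 − r)/24.

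| Rescue week r | Minimum f | Untabulated, minimum follow-up | Untabulated, to Week 24 |
|---|---|---|---|
| 4 | 12 | 8/12 = 67% | 20/24 = 83% |
| 8 | 12 | 4/12 = 33% | 16/24 = 67% |
| 12 | 16 | 4/16 = 25% | 12/24 = 50% |
| 16 | 20 | 4/20 = 20% | 8/24 = 33% |
| 20 | 24 | 4/24 = 17% | 4/24 = 17% |

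**4. One SAE after rescue, none otherwise.** The table shows 0 instead of 1/3 = 33.3%, 1/6 = 16.7% or 1/8 = 12.5%.

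**5. Laboratory and ECG visits.** Post-baseline labs are at Weeks 4, 12 and 24 and ECGs at Weeks 4 and 24 (SAP 9.5.1.4). After rescue at Week 4, the Week 12 labs and any Week 24 or exit labs and ECG are untabulated on any reading. If the cut is applied by calendar date and rescue falls on the visit day, the Week 4 values go too: 0 of 3 labs and 0 of 2 ECGs kept, against 1 of 3 and 1 of 2.

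**6. Cohort of 6, k patients rescued (assumed), the rest completing 24 weeks.** Share of collected patient-weeks lost = k(f − r)/[24(6 − k) + kf].
- k = 1: 8/132 = 6.1% (Week 4), 4/132 = 3.0% (Week 8), 4/136 = 2.9% (Week 12), 4/144 = 2.8% (Week 20).
- k = 3: 24/108 = 22.2%, 12/108 = 11.1%, 12/120 = 10.0%, 12/144 = 8.3%.

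**7. Illustration of the effect on incidence.** Assume a 30% 24-week incidence and constant hazard. The tabulated probability is 1 − 0.7^(r/24) and the collected one 1 − 0.7^(f/24).
- Rescue at Week 4: 0.058 against 0.163, a loss of 0.106 of a patient, or 1.8 points in a cohort of 6.
- Rescue at Week 20: 0.257 against 0.300, a loss of 0.043, or 0.7 points.
- If patients stay to Week 24, the loss is (0.30 − tabulated)/6: 4.0 points for rescue at Week 4, down to 0.7 at Week 20.

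**8. Illustration against Table 2.** Assume p = 0.2 over 24 weeks, constant hazard, a share q = 0.5 rescued on day t, and follow-up to Week 24. Each patient's tabulated probability is (1 − q)p + q[1 − (1 − p)^((t − 1)/167)]: 0.1177 for t = 28 and 0.1525 for t = 84. With n = 8, the chance that the table shows at least one such patient falls from 0.832 to 0.633 (t = 28) or 0.734 (t = 84).

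**9. Day of rescue.** The general rule removes data from the rescue itself onward; the TEAE window runs up to it. Neither says whether measurements taken before the injection that day are kept. One rescue criterion needs only a single visit with a loss of more than 10 letters. If rescue is given that day, the cut is by date, baseline was the best visit and the visit was scheduled, that loss leaves the letter-loss table of section 9.7.1.6.2. Under the two-visit criteria the first visit's value survives if that visit was scheduled.

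**The case against.** The strongest reply is textual. The separate AE and TEAE wording, with the remark about the TEAE definition, suggests that for AEs the cut may work only through TEAEs. The AE and SAE tables would then be complete and steps 4, 7 and 8 would fall away. This cannot be excluded, but it has to be inferred against a sentence covering all safety data in tables. It would not rescue the laboratory, ECG, vital-sign or fellow-eye tables.

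Second, nothing collected is lost. Listings keep every AE, SAE and death, there are about 25 open-label patients, and no group comparison is planned. This limits the seriousness, but listings give no incidence by cohort. The listing of events leading to study termination is also restricted to treatment-emergent events.

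Third, Table 2 concerns observing an event, and an SAE in a listing has been observed. That is fair: step 8 concerns what the tables show, not detection or dose escalation.

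Two further points stand. The denominator argument applies to AE percentages; shift tables use patients with values at the visit, so censored patients leave those denominators too. The rescue-day BCVA example needs several conditions at once. A display up to rescue is legitimate in a single-dose study; the weakness is that it is the only one stated.

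**Conclusion.** The concern holds and should be fixed. As worded, the SAP removes from its safety tables data that the protocol requires to be collected after rescue, whatever the eye, body system or seriousness. Tabulated AE incidence and worst severity can only equal or fall below what was collected.

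The share of a rescued patient's minimum follow-up that is lost runs from 17% to 67%. The effect on AE counts is unknown because the documents give no rescue rate or event timing; it is zero if every event starts before rescue. Under the 30% illustration it is about 0.7 to 4.0 points per rescued patient in a cohort of 6, where one patient is 16.7 points.

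The conclusion on AE tables rests on reading section 9.7.1.6 as governing section 9.7.1.6.1. If that was not intended, the two sections still need reconciling. No effect on dose escalation is claimed.

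**What to change.** Replace the last paragraph of SAP 9.7.1.6 with:

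> AEs, SAEs, non-study-eye data and systemic safety data (labs, ECG, vital signs) will be tabulated from study drug administration through study exit regardless of rescue, using the FAS, with post-rescue data flagged. The same tables, and study-eye safety data, will also be shown up to the first rescue. Assessments made before the injection on the day of rescue count as pre-rescue.

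In 9.7.1.6.1, state which data each AE and TEAE table uses, give the TEAE window the same rescue-day rule, and name the FAS as denominator in place of the undefined Safety Analysis Set. Patient-weeks of follow-up per cohort would help the reader; exposure-adjusted rates are optional.

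The cost is SAP wording and a second version of the affected tables; no new data are needed. Some events due to the rescue drug will enter the all-follow-up tables, which the flag and the up-to-rescue display handle. Later by-visit laboratory, ECG and vital-sign summaries will remain incomplete, because rescued patients may leave at different times, so the number contributing at each visit should be shown. If the table count must be kept down, AE and SAE tables regardless of rescue come first.
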